5.5.1 Reasons for Withdrawal

Subjects are free to withdraw from participation in the study at any time upon request.

An investigator may terminate a study subject's participation in the study if:

- Any adverse event (AE) or other medical condition or situation occurs such that continued participation in the study would not be in the best interest of the subject.
- The subject meets an exclusion criterion (either newly developed or not previously recognized) that precludes further study participation. For example, the participant is found to be ineligible after enrollment (e.g., prior household member enrolled).

5.5.2 *Handling of Subject Withdrawals or Subject Discontinuation of Study Intervention*

Participants who request to drop out will be given the option to withdraw from participation in the intervention only, but to still participate in the follow-up evaluations. Participants who refuse this offer and request to completely withdraw from the study will no longer be contacted. However, previously obtained data will be retained with subject consent.

We will not recruit replacement participants for drop-outs. Persons who withdraw as a result of an adverse event will be referred for appropriate care.

5.6 Premature Termination or Suspension of Study

This study may be prematurely terminated if, in the opinion of the investigator, the sponsor or the IRB there is sufficient reasonable cause. Written notification, documenting the reason for study termination, will be provided to the investigator and/or sponsor by the terminating party. Circumstances that may warrant termination include, but are not limited to:

- Determination of unexpected, significant, or unacceptable risk to subjects.
- Insufficient adherence to protocol requirements.
- Failure to obtain sufficient follow-up data to evaluate the effectiveness of the intervention.

If the study is prematurely terminated or suspended, the sponsor will promptly inform the investigators/institutions, and the regulatory authority(ies) of the termination or suspension and the reason(s) for the termination or suspension. The IRB/IEC will also be informed promptly and provided the reason(s) for the termination or suspension by the sponsor or by the investigator/institution, as specified by the applicable regulatory requirement(s).

6 STUDY INTERVENTION

6.1 Study Behavioral or Social Intervention(s) Description

Participants will be randomized to receive usual care treatment through their tobacco quitline or the enhanced intervention combining usual care with a multi-modal behavioral oral health promotion program.

Usual care: Usual care participants will receive standard quitline counseling as described below (section 7.3):

- Written usual care resources offered by mail and Internet, as consistent with the standard quitline intervention program
- Access to a standard course of nicotine replacement therapy, if medically appropriate.

All materials are focused on tobacco cessation and do not include oral health promotion materials. Average call duration in the participating quitlines ranges from 13.76 minutes (Oregon) to 14.36 minutes (Nebraska). To control for the effects of the texting intervention, we will augment usual care with an attention-matched texting outreach focused on health behaviors other than smoking cessation or oral health promotion. Additional detail on the texting program is included appendix G.

The intervention protocol for the usual care counseling is proprietary and is not described in this protocol. Standard program components for each state's program is detailed in the table below. Additional information regarding call timing can be found in section 7.3.

	Phone Counseling	Web-based Intervention	Text Messaging	Nicotine Replacement
Oregon	4 proactive calls	Yes	Not currently	2 week supply patch/gum to uninsured
Nebraska	5 proactive calls	Yes	Not currently	None
Louisiana	5 proactive calls	Yes	Not currently	2 week supply patch or gum

Enhanced (Experimental) Intervention: Experimental participants will receive the following care:

- usual care tobacco quitline counseling
- additional counseling content focused on oral health promotion
- mailed oral health promotion materials
- access to the OralHealth4Life.com log-in secured website and
- a series of proactively delivered oral health promotion text messages.

Materials also include referral information for local, low cost professional dental care services, a toothbrush, floss, and other oral health hygiene materials. Additional detail on the intervention and timing of the contacts is summarized below in section 7 and outlined in Appendix A (Schedule of Events).

Intervention content is included in Appendix G (Oral Health 4 Life booklet), Appendix F (Counseling Protocol and Training Materials), Appendix G (Text Messages and Delivery Schedule), and at www.OralHealth4Life.com (*website access is restricted during the study period*).

6.2 Administration of Intervention

The timing of each intervention component is detailed below in section 7 (Study Schedule), Diagram 1 (Study Flow for RCT), and Appendix A (Schedule of Events).

All phone counseling will be delivered by quit coaches at Alere Wellbeing. Oral health counseling will be integrated into each tobacco cessation counseling call following a structured intervention protocol. Each participant may receive up to 5 integrated oral health promotion-tobacco cessation counseling calls.

Written oral health materials and other study-provided oral health aids (e.g., toothbrush, floss) will be mailed to participants by staff at GHRI. Materials will be mailed within 1-2 days after participants enroll in the study.

Participants will have secure access to the OralHealth4Life website (OralHealth4Life.com) starting on the day of their enrollment. Directions for accessing the site will be provided during the initial counseling call and included in the written study materials provided by mail. Following the study, open-access copies of the website will be made available to participants randomized to both study arms.

GHRI staff will oversee delivery of the intervention text messages, which will be sent on a standardized schedule (see section 7.3). Participants will receive up to 16 total text messages during the period ranging from the day before their chosen target smoking Quit Date to 22 days following their target Quit Date. Persons who request to stop receiving text messages will be opted out of receiving messages at that time.

6.3 Procedures for Training Interventionists and Monitoring Intervention Fidelity

Usual care counselors will be trained by Alere using their standard protocols and procedures. These counselors will also be informed about the basic study overview in order to field general questions from participants, but will not be trained on or have access to the oral health counseling protocol.

Counselors delivering the enhanced intervention will be trained to deliver usual care smoking intervention and the oral health counseling by Alere staff. Training in the oral health content will be led by Alere staff, under the direction of Drs. [name] and [name]. The additional oral health counseling will be added to the usual care counseling for subjects receiving the enhanced intervention.

Calls (usual care and enhanced) will also be audio taped per Alere's standard protocol and a random sample involving at least 10% of calls will be monitored and coded for fidelity to the study protocol. More calls will be monitored, as needed, based on observation of interventionist drift or as needed to monitor the enhanced intervention, in particular.

6.4 Assessment of Subject Compliance with Study Intervention

Compliance with the counseling will be monitored through automated tracking of participants' quitline calls (e.g., number of calls taken, duration of calls).

Participants will also be surveyed about their utilization of the written content, log-in secured website, and text messages.

7 STUDY SCHEDULE

7.1 Screening (Call 1, Day 0)

Persons who are eligible for services through one of the participating quitlines and preliminarily eligible for the study based on eligibility criteria assessed as part of the standard quitline registration process will be informed of the study and invited participate. They will be screened for eligibility at the time of their initial quitline registration call. The screening will be conducted by phone by Alere staff trained in the study procedures. Respondents will answer each screening eligibility question. If a caller refuses to answer any screening questions or fails to meet the inclusion criteria above, they will be deemed ineligible. The screening assessment will continue until a person is deemed ineligible or the entire survey is completed.

Eligible persons will be invited to learn more about the study and will be read a scripted informed consent. Persons who give verbal consent to join the study will then complete a baseline assessment by phone and be randomized to treatment. Following enrollment, participants will be mailed a written copy of the consent form for their records (Appendix H).

Alere staff will document the consent process for each person including whether they agreed to provide consent to be screened [yes/no] and/or to enroll in the study [yes/no].

Each person will receive a screening disposition of:

- Ineligible (with the reason coded)
- eligible but refused
- or eligible and enrolled

7.2 Enrollment/Baseline (Call 1, Day 0)

Following completion of the consent process, participants will complete a baseline phone interview and be randomized to treatment using the automated algorithm. Persons who are randomized to usual care will then be transferred to a usual care quit coach. The quit coaches will have no training in or exposure to the enhanced intervention protocol in order to prevent contamination. Persons assigned to the experimental arm will receive counseling from a quit coach in Alere's Research Implementation Unit who has been trained in the enhanced intervention protocol. [NOTE: This contact occurs during the same registration call as the screening, consent, and baseline interview.]

7.3 Intermediate Visits

7.3.1 *Control Intervention*

Participants randomized to the control condition will receive standard quitline counseling, plus usual care resources offered by mail, Internet, as consistent with the standard quitline intervention program. All materials are focused on tobacco cessation and do not include oral health promotion content. The intervention protocol for this counseling is proprietary and is not detailed here. All standard intervention materials will be delivered by Alere per standard procedures. Control participants will also receive an attention-matched texting program. Texts will be sent on the same delivery schedule detailed below for enhanced intervention participants.

The call schedule is tailored for each person, based on their availability, planned quit date(s), and continued program engagement, but generally follows the timeline below:

- Call 1: Enrollment call/treatment session 1 (pre-target Quit Date [QD])
- Call 2: QD or QD +1 day (~week 1-2 after Call 1)
- Call 3: QD + 1-2 weeks (~week 2-4 after Call 1)
- Call 4: Call 3 + 3 weeks (~week 4-6 after Call 1)
- Call 5: Call 4 + 3 weeks (~week 6-10 after Call 1)

Following completion of the first counseling call, usual care participants will receive a welcome letter, \$30 thank you, and a written copy of the study consent form for their records (Appendix H). These materials will be mailed by GHRI study staff.

7.3.1.1 Post-Study Access to Website

Following completion of the study, control arm participants will be sent a link via text and mail to an open-access copy of the study intervention website. Anonymous administrative usage statistics will be collected (e.g., number of page hits, time spent per page, etc.) for the control arm copy of the open-access website.

7.3.2 *Enhanced Intervention: (Usual Care + Oral Health Promotion)*

7.3.2.1 Phone Contact 1 & Mailed Materials

Participants assigned to the enhanced intervention will receive standard quitline counseling plus additional counseling focused on oral health promotion. Following completion of this call, participants will be mailed usual care tobacco cessation materials by Alere Wellbeing staff. GHRI staff will mail an oral health promotion packet to the subjects randomized to receive enhanced intervention. The packet will include a study welcome letter, a written oral health booklet (Oral Health 4 Life: A Quick Guide to

Better Oral Health) developed for study participants, access to the OralHealth4Life.com log-in secured study website which includes additional oral health promotion resources and information, oral health promotion supplies (e.g, toothbrush, toothpaste, floss), a copy of the written consent form, and a \$30 thank you.

Additional behavioral intervention will be delivered during future phone counseling sessions as outlined in the interventionist training materials and via text, as described below.

7.3.2.2 Phone Contact 2-5

Participants will be contacted by phone per the standard Quit for Life tobacco cessation program timeline and outreach protocol. This is a 4 or 5 call program, depending on the state contract. Call 1 occurs prior to the quit date. Call 2 occurs within a day of the target quit date (TQD). Calls 3-5 are typically scheduled following the TQD. During each of these counseling calls, participants will receive standard cessation counseling plus additional counseling to promote better oral health outcomes. This includes advising all participants to schedule a dental check-up/cleaning in the near future, advising them to brush and floss daily, providing information about the health benefits of routine oral hygiene and risks of tobacco and alcohol to oral health; and recommending participants engage in strategies designed to both help them stop smoking and promote oral health (e.g., promoting use of sugar free gum, tooth brushing, and flossing as strategies for distracting oneself from smoking and managing cravings). The oral health promotion counseling is designed to be 'front loaded' in calls 1-3, with booster content reviewed in calls 4 and 5. Additional detail is included in the Oral Health 4 Life Counseling Protocol and Training Materials (Appendix F).

7.3.2.3 Text Messaging (Enhanced Intervention Group)

Participants will receive a series of text messages designed to reinforce the pro-oral health messaging delivered by the quitline counselors and promote use of the Oral Health 4 Life log-in secured website. The messages and timing were developed through an iterative process involving focus group feedback and feedback from individual smokers to ensure appropriate content, timing, and frequency of contacts. Messages are intentionally brief and do not exceed the maximum 160 SMS character limit, to prevent wrapping across multiple text messages or truncation. Message content was designed to be responsive to smokers' specific requests for information and encouragement for behavior change. Message timing was also based on feedback provided by smokers, although the messaging will be less frequent than the daily schedule focus group participants requested.

Text messages will be delivered on a standardized schedule based on each person's initial target tobacco quit date (TQD), as follows:

- One day prior to the TQD

- One message per week from TQD + 1 week to TQD + 8 weeks
- One message every 2 weeks from TQD + 14 weeks through TQD + 22 weeks.

The same schedule will be used to send text messages in the control arm (see message content in Appendix G).

To ensure consistent delivery and adherence to the planned schedule, GHRI staff will set up automatic delivery of all messages within 3 days of enrollment. All text messages will be managed through an online text messaging vendor program.

Participants will be informed not to respond to text messages. If they do, they will receive an automated reply which informs them we cannot respond directly to their text and directs them to the Oral Health 4 Life log-in secured website or to a quitline counselor for more information.

Participants can request to discontinue receiving text messages and remain enrolled in the study.

7.3.2.4 Website

Participants in the enhanced intervention will receive access to the OralHealth4Life.com log-in secured website. This site includes similar, but expanded, content to that in the Oral Health 4 Life pamphlet including detailed information on where to find local, low-cost professional dental care in each participating state. Content was developed through an iterative process including feedback from oral health specialists (dentist, periodontist, & oral pathologist), behavioral scientists, and smokers participating in focus groups and individual usability evaluation assessments. Access to the site will require a log-in ID and password, in order to track individual use of the website.

7.3.2.4.1 *Post-Study Access to Website*

Log-in requirements are known to present a barrier to use. Therefore following completion of the study, enhanced intervention participants will be sent a link via text and mail to an open-access copy of the study website. Anonymous administrative usage statistics will be collected (e.g., number of page hits, time spent per page, etc.) for the intervention arm copy of the open-access website..

7.3.2.5 Follow-up Assessments

Follow-up phone surveys will be conducted by the GHRI Survey Research Program at 2 and 6 months post-enrollment. Each participant will receive a reminder letter and text message approximately one week prior to their interview due date. Professional interviewers will then contact each person by phone to complete the standardized interview.

Persons who are reached by phone but who decline to participate in the full interview will be asked to provide information on each of the main outcomes of interest. Each

person who completes an interview (full or abbreviated) will be mailed a thank you letter and \$30 check or gift card as a thank you for their time.

During each follow-up contact, survey staff will confirm that the contact information on file is correct for each participant (mail address, cell phone number, home number, and email address).

Persons who cannot be reached within 2 weeks of their scheduled due date will be mailed a written survey to complete and return by mail. Persons who are not reached by phone and do not return the written survey within 4 weeks post-due date at 2 month follow-up or 6 weeks post-due date at 6 month follow-up will be coded as unable to reach. Other response options include: refused, deceased, and unknown.

7.4 Withdrawal Visit

Participants who ask to withdraw from all future study contacts (intervention and assessment) will be allowed to do so. We will not conduct an early termination visit, but individuals will be asked their reason for drop out and may be asked to provide information on the primary outcome variables if drop out occurs within ~ one month of a scheduled follow-up assessment. These interviews will be conducted by study staff at GHRI.

7.5 Unscheduled Visit

Since phone counseling is delivered proactively by tobacco quitline staff in accordance with a standardized timeline, there will be no unscheduled intervention visits. Per the quitline protocol, participants can call in at any time to receive ad-hoc tobacco cessation counseling. If they occur, these contacts will be separate from the intervention delivered as part of this trial, but their occurrence will be tracked by Alere for study purposes. Oral health counseling will be included in these calls. If the quit coach neglects to deliver the oral health counseling, a call back will be made to attempt to deliver this content.

8 STUDY PROCEDURES /EVALUATIONS

Standard operating procedures for the study will be detailed in the Manual of Procedures (MOP), which will be provided to study staff prior to study start-up. Overviews of the procedures are provided here. Data collected will be directly entered into our electronic data collection system.

Additional detail regarding study procedures are included in sections 3.2.1, 5, 6, and 7 above. Baseline and follow-up surveys can be found in the Appendices.

9 ASSESSMENT OF SAFETY

9.1 Specification of Safety Parameters

This is a minimal risk behavioral intervention. Nevertheless, adverse events (AEs) will be recorded and reported over the course of the study as outlined below:

9.1.1 *Unanticipated Problems*

The Office for Human Research Protections (OHRP) considers unanticipated problems (UP) involving risks to subjects or others to include, in general, any incident, experience, or outcome that meets all of the following criteria:

- unexpected in terms of nature, severity, or frequency given (a) the research procedures that are described in the protocol-related documents, such as the IRB-approved research protocol and informed consent document; and (b) the characteristics of the subject population being studied;
- related or possibly related to participation in the research (“possibly related” means there is a reasonable possibility that the incident, experience, or outcome may have been caused by the procedures involved in the research); and
- suggests that the research places subjects or others at a greater risk of harm (including physical, psychological, economic, or social harm) than was previously known or recognized.

9.1.2 *Adverse Events (AE)/Serious Adverse Events (SAE)*

An adverse event is any untoward or unfavorable medical occurrence in a human subject, including any abnormal sign (for example, abnormal physical exam or laboratory finding), symptom, or disease, temporally associated with the subject's participation in the research, whether or not considered related to the subject's participation in the research.

9.1.3 *Expected Adverse Reactions*

Persons who visit a dental professional or change their daily oral hygiene regimen may experience temporary changes in gum bleeding or tooth sensitivity.

Because the study will use phone, mail, and Internet to communicate with participants, it is possible that others may learn of their participation in this study (e.g., breach of confidentiality). Expected AE's in this study are generally considered to be mild (easily tolerated) to moderate (discomfort with some interference in usual activities), but not severe (incapacitating).

Persons who stop smoking may experience symptoms of nicotine withdrawal.

See additional discussion of potential adverse reactions in section 2.3.1(Potential Risks).

9.2 Time Period and Frequency for Event Assessment and Follow-Up

Unanticipated problems will be recorded in the data collection system throughout the study.

The PI will record all reportable events with start dates occurring any time after informed consent is obtained until 7 (for non-serious AEs) or 30 days (for SAEs) after the last day of study participation. At each study visit, Alere staff will inquire about and record the occurrence of AE/SAEs since the last contact. Events will be followed for outcome information until resolution or stabilization.

9.3 Characteristics of an Adverse Event

9.3.1 Relationship to Study Intervention

AE's deemed possibly related to the study intervention by Alere staff and [name] will be shared with the PI ([name]), who will make a final determination whether each AE is due to study involvement. The following guidelines will be used. [NOTE: Some AE's associated with quitting smoking, but which are not clearly associated with study participation will not be passed on to the PI by [name] or Alere staff. For example, AE's which are deemed to be related to the stop smoking medication use. These will be managed per Alere's standard internal protocols for medical oversight.]

- Associated – The event is temporally related to the study participation and no other etiology explains the event.
- Not Associated – The event is temporally independent of study participation and/or the event appears to be explained by another etiology

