9.3.2 Expectedness of SAEs

The NIDCR Medical Monitor and the Study PI will be responsible for determining whether an SAE is expected or unexpected. An adverse event will be considered unexpected if the nature, severity, or frequency of the event is not consistent with the risk information previously described for the intervention.

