9.4 Reporting Procedures

9.4.1 *Unanticipated Problem Reporting to IRB and NIDCR*

Incidents or events that meet the OHRP criteria for unanticipated problems will be reported to the IRB. Unanticipated problem reports will include:

- appropriate identifying information for the research protocol, such as the title, investigator's name, and the IRB project number;
- a detailed description of the adverse event, incident, experience, or outcome;
- an explanation of the basis for determining that the adverse event, incident, experience, or outcome represents an unanticipated problem;
- a description of any changes to the protocol or other corrective actions that have been taken or are proposed in response to the unanticipated problem

Reporting of Unanticipated Problems to NIDCR is accomplished by submission of an Unanticipated Problem Report via fax or email to Rho Product Safety. Once submitted, Rho Product Safety will send a confirmation email to the investigator within 1 business day.

UP Reporting Contact Information:

- Product Safety Hot Line: [name]
- Product Safety Fax Line: [name]
- Product Safety Email: [contact]

9.4.2 *Serious Adverse Event Reporting to NIDCR*

Any AE meeting the specified Serious Adverse Event criteria will be submitted on an SAE form to NIDCR's centralized safety system via Rho Product Safety. This report may be sent by fax or email. Once submitted, Rho Product Safety will send a confirmation email to the investigator within 1 business day. The investigator should contact Rho Product Safety if this confirmation is not received. This process applies to both initial and follow-up SAE reports.

SAE Reporting Contact Information:

- Product Safety Hot Line: [name] (International: [contact])

- Product Safety Fax Line: [name] (International: [contact])
- Product Safety Email: [contact]

General questions about SAE reporting can be directed to the Rho Product Safety Help Line (available 8:00AM – 5:00PM Eastern Time) at [name] or [contact].

The study PI or Project Manager will complete a Serious Adverse Event Form within the following timelines:

- All deaths and immediately life-threatening events, whether related or unrelated, will be recorded on the Serious Adverse Event Form and sent by fax or email within 24 hours of site awareness.

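### The NOTE in 9.3.1 keeps some quitting-related AEs from the PI with no exception for serious ones, and it is not reconciled with the SAE provisions in 9.2, 9.3.2 and 9.4.2

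*Combined protocol and SAP*

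**What the plan says.** Section 9.2 places first contact with events at Alere: "At each study visit, Alere staff will inquire about and record the occurrence of AE/SAEs since the last contact". It also gives the PI a recording duty: "The PI will record all reportable events with start dates occurring any time after informed consent is obtained". The recording window runs to 7 days after participation for non-serious AEs and 30 days for SAEs.

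Section 9.3.1 then sets out what reaches the PI for a causality decision. AEs "deemed possibly related to the study intervention by Alere staff" and by a second person, whose name is removed from the public text, are shared with the PI. The bracketed NOTE carves out some AEs linked to quitting, "which are not clearly associated with study participation will not be passed on to the PI" by that person or by Alere staff. Its example is AEs put down to stop-smoking medication. Events in this group are handled under Alere's "standard internal protocols for medical oversight".

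Section 9.3.2 says: "The NIDCR Medical Monitor and the Study PI will be responsible for determining whether an SAE is expected or unexpected". It applies no relatedness filter and names no delegate for the PI.

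Section 9.4.2 says: "Any AE meeting the specified Serious Adverse Event criteria will be submitted on an SAE form". It adds: "The study PI or Project Manager will complete a Serious Adverse Event Form within the following timelines". The limits are 24 hours from site awareness for deaths and immediately life-threatening events and 72 hours for other SAEs. Both apply whatever the causal relationship.

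**The concern.** The NOTE sorts events by how clearly they are tied to study participation. For serious events, 9.4.2 makes that question irrelevant to reporting. If Alere staff apply the NOTE as written to a serious event that they attribute to medication or to quitting, they would not send it to the PI. Yet the PI shares responsibility for judging whether that event is expected.

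Three things are at stake: the expectedness judgement, the completeness of the PI's record, and the timeliness of the SAE report if it depends on somebody else noticing the event. Section 9.5 also lets the PI suspend enrolment because of the presence, type or frequency of SAEs, which presupposes that the PI sees them. That is not the only safeguard, since the IRB, NIDCR and the DSMB can each require a halt. Efficacy is not at stake: neither primary outcome nor any planned analysis uses these data.

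**Working it through.** No arithmetic applies. The check follows one case through the sections: a serious event that Alere staff learn of on a counselling call and attribute to stop-smoking medication.

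1. **Is it an AE?** Yes. Section 9.1.2 defines an AE without regard to relatedness.
2. **Is it still an AE once it is serious?** Yes. Section 9.4.2 describes an SAE as an AE that meets the specified criteria, so SAEs are a subset of AEs. The argument does not depend on what those criteria are.
3. **Does the 9.3.1 NOTE cover it?** Read literally, it can. The NOTE speaks of some AEs, gives medication-attributed events as its example, and has no seriousness limit. No other section supplies one.
4. **Must it be filed?** Yes. Section 9.4.2 requires this within 24 or 72 hours, irrespective of relationship. Either the PI or the Project Manager may complete the form.
5. **Must the PI judge expectedness?** Yes, with the NIDCR Medical Monitor, under 9.3.2. This is the plainest mismatch, because the duty attaches to any SAE and the PI needs to know of the event to perform it.
6. **Must the PI record it?** Section 9.2 covers reportable events but does not define the term. Section 9.4.2 makes every SAE reportable, so the duty applies to this event through 9.4.2. For non-serious AEs, 9.2 alone shows no inconsistency with the NOTE.
7. **Who carries the event from Alere to the people who must act?** The Protocol Summary lists Alere as one of two research sites, so site awareness can begin there. Section 16.6 places the Project Manager at GHRI, the other site. The hand-off to the PI described in 9.3.1 is for events thought possibly related, and it has no time limit. For the event in this example, the sections on safety do not say who tells the Project Manager or the PI, or how soon.

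Steps 3 and 5 pull in different directions unless another channel brings the event to the PI. Steps 3 and 4 can both be followed, but only if somebody other than the PI is told in time.

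**The case against.** The strongest reply is that the NOTE was never meant for serious events. It stands in a section on causality, while SAEs have their own provisions, and a specific SAE rule would ordinarily govern SAEs. The effects the protocol foresees from quitting and from nicotine replacement (2.3.1) are withdrawal symptoms, headache, nausea, poor sleep and patch-site irritation. Section 9.1.3 describes expected AEs as generally mild to moderate. This may well be the intention, but the text does not say so, and the staff who must apply the NOTE are at a different organisation from the Project Manager.

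A reader might infer three stronger things, none of which the documents support.

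- **That the NOTE directly contradicts the PI's duties.** The NOTE restricts only what Alere staff and the intermediary pass on. The Project Manager may file under 9.4.2 and could inform the PI without breaching it. The link to 9.2 exists only through 9.4.2, which may itself be meant to prevail over the NOTE. Unreconciled is the right description.
- **That SAEs in this group go unreported.** Section 9.4.2 still requires every SAE to be filed, and the NOTE does not suspend it.
- **That no channel exists between the sites.** Table 1 lists regular data feeds from Alere to GHRI. Section 16.3 counts safety data among the study data. GHRI conducts the 2- and 6-month surveys, and Appendix A appears to schedule assessment of unanticipated problems at those contacts. The Manual of Procedures, which was not supplied, may describe a route, as may the role of the person whose name is removed.

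What remains is that none of these channels, as described, is tied to the SAE deadlines, and none removes the instruction in the NOTE.

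**Conclusion.** The point holds as an unreconciled set of safety-reporting instructions. Followed literally, the NOTE can keep a serious event from the PI, or delay it, on a criterion that 9.4.2 excludes for SAEs.

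The size is modest. The documents give no SAE rate, so no count of affected events can be stated. It is probably small: section 9.1 describes a minimal-risk behavioural intervention, the NOTE covers only some AEs, and quitline-supplied nicotine replacement is limited (6.1). Louisiana offers a two-week supply, Oregon offers one to uninsured callers only, and Nebraska offers none. Filing remains mandatory and other bodies can halt the study.

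The conclusion rests on two assumptions: that AE in the NOTE carries the protocol's own meaning, which includes SAEs, and that no unsupplied document already limits the NOTE. If the Manual of Procedures does limit it, the practical risk largely disappears, but the protocol should still say so. The amendment is worth making because it is cheap and concerns safety.

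**What to change.** Reconcile 9.3.1 with 9.2, 9.3.2 and 9.4.2:

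- State in 9.3.1 that the NOTE applies only to non-serious AEs and does not limit 9.2, 9.3.2 or 9.4.2.
- State that Alere staff forward every event meeting the SAE criteria, in either arm and whatever its attributed cause, to the Project Manager and the PI in time for the existing 9.4.2 deadlines. Section 16.6 already has all staff report deviations to the Project Manager, who informs the PI, and could serve as the model.
- If the Manual of Procedures already provides this, add a cross-reference to it.

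The cost is a wording amendment of a sentence or two with IRB review (15.2), a short notice to quitline staff, and possibly a few more reports for the Project Manager and the PI. No outcome, analysis or sample size changes.
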